4.3.9 SCLERAL CONTACT LENSES

Zen™ RC scleral lenses (non-coated, and Hydra-PEG coated) to be used in this study are approved by Health Canada and are commercially available (license #96602). They are manufactured using the Boston XO material (Health Canada license #71386). All lenses will be worn during the day only. Lenses will be fitted according to manufacturer's recommended guidelines and participants will proceed in the study only if a suitable fit with the lenses can be obtained. This type of conventional lens design will be fitted on both eyes. Appendices 14 and 15 (Package insert for Boston XO and Zen™ RC Fitting Guide respectively).

4.3.10 CONTACT LENS CARE SYSTEM AND ASSESSMENT

The lens care systems that will be used by the investigator/participants during the trial fitting and the dispensing of the scleral contact lens in this study are: Clear Care Disinfecting Solution (Health Canada license #02245661), Boston Simplus Comfort Formula Conditioning solution (Health Canada license #02019868), Sensitive Eyes Saline Plus (Health Canada license #6208410) and Minims Saline (Health Canada license #02148501) (Bausch + Lomb, Rochester, NY, USA). Clear Care and Disinfecting Solution will be used to disinfect the scleral contact lens overnight (minimum of 6 hours) of disinfection. Boston Simplus Comfort Formula Conditioning solution will be used to provide lubrication (initial comfort) on the front surface of the lens before lens application and also to store the lens when not in use. The lenses will be rinsed thoroughly with Sensitive Eyes Saline Plus and filled with Minims Saline before insertion. Sodium fluorescein strips (Health Canada license #02179539) (Fluorets; Laboratoire Chauvin, Aubenas, France) will be used during the trial fitting of the scleral contact lenses.

Participants will be carefully instructed following the manufacturers' recommendation for caring for the lenses before dispensing.

4.3.11 STUDY QUESTIONNAIRES-ANALOG RATING SCALES

The following questionnaires will be used in the study.

As part of the recruitment and the baseline measurements (screening visit), Ocular Surface Disease Index (OSDI) and Standardized Patient Evaluation of Eye Dryness (SPEED) questionnaires will be used to determine the severity and frequency of the DE condition. It will also be used to determine eligibility of the participants (Appendix 4 and 5). Contact Lens Dry Eye Questionnaire 8 (CLDEQ-8) will be used to assess ocular symptoms with the scleral contact lenses at the end of each study visit. (Appendix 8) Contact Lens Impact on Quality of Life (CLIQ) will be used to assess the impact of contact lenses on their daily lives during the wearing schedule. The Contact Lens Dry Eye Questionnaire 8 (CLDEQ-8), Contact Lens Impact on Quality of Life (CLIQ) (Appendix 9) and wearing habit/experience log along with the subjective grading scales (Appendix 10) will be given to the participants to fill out for each week wearing the scleral lenses. The questionnaires will be returned to the investigator during the follow up visits. The standard method of recording the CLIQ questionnaire will be used in the study.

Comfort, vision, dryness, burning and overall preference rating scales (0-100) will be used to assess the subjective responses for each of the contact lenses. These subjective ratings will be done on a weekly basis (at home) and at the end of each study visit.

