4 MATERIALS AND METHODS

4.1 STUDY DESIGN

4.1.1 OVERALL DESIGN

This will be a prospective, dispensing cross over study design involving five visits.

The first visit will involve screening, baseline measurements and trial fitting of scleral lenses. At this visit, participants may be wearing their habitual contact lenses (if any) as prescribed by their Optometrist/Ophthalmologist.

The second visit will be a dispensing visit of one of the pairs of the scleral contact lens designs (with or without Hydra-PEG, randomly assigned) and a single follow up visit after 8-10 hours of lens wear in a day, four weeks later (third visit). A washout period of a minimum of 48 hours will be applied between lens types. The fourth and fifth visits will be for the other scleral contact lens visits (delivery and after 4 weeks).

Scleral contact lenses to be worn in this study will be made of Boston XO material (with and without Hydra PEG) approved by Health Canada for commercial purposes. The scleral contact lenses will have a diameter of 14.8-15.4mm. The manufacturer's recommended guidelines will be used to select and fit these lenses, with an expected corneal clearance between 250 μ m to 350 μ m. As to which of the two scleral contact lenses are being assessed, both the investigator and the participant will be masked as the Optometric assistant will provide the lenses in an unlabelled case.

Masking the investigator will prevent bias when measuring the primary outcome variables and analyzing the data.

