4.5.3 FOLLOW-UP VISIT

Following the four weeks of the contact lens wear, the participant will present at the follow-up visit (visits 1-2, 2-2). The lens will be examined with the slit lamp biomicroscope. This will be

followed by visual acuity and imaging with Spectralis OCT (to assess corneal clearance and cornea thickness).

The investigator will carefully remove the contact lens from the eye and immediately collect the tears from the lens bowl for tear analysis. Levels of protease and cytokines in the tears will be assessed.

Slit lamp biomicroscopy mounted camera will be used to assess the corneal integrity and staining. This will be followed by imaging with the Keratograph 5M (for staining) and Spectralis OCT for corneal thickness measurements.

The questionnaire administered (CLDEQ-8, CLIQ and wearing habit/experience along with subjective grading scales) will be collected and reviewed for completeness.

The above-described procedures will be followed for all the lenses to be used in the study.

Table 2 lists a summary of procedures to be conducted at scheduled visits.

Table 2: Summary of procedures at scheduled visits

| Visit | Procedure | Instrument/ application | Form (Appendix #) |
|---|---|---|---|
| Screening, Baseline visit and Trial Lens Fitting (Visit 0-0) | Informed Consent | - | ICL (2) |
| | Demographics & Med. History | - | Screening Form (3) |
| | Ocular surface disease | Self-Administered Questionnaire | OSDI questionnaire (4) |
| | Evaluation of Eye Dryness | Self-Administered Questionnaire | SPEED questionnaire (5) |
| | Vision assessment | LogMAR chart | Study Visit Form for Scleral Lenses (6) |
| | Osmolarity | Tearlab osmolarity system | Study Visit Form for Scleral Lenses (6) |
| | Level of protease (MMP-9) | InflammaDry | Study Visit Form for Scleral Lenses (6) |
| | Tears from ocular surface | Micropipette tear collection kit | Study Visit Form for Scleral Lenses (6) |
| | Ocular surface imaging | Keratograph 5M (K5M) | Study Visit Form for Scleral Lenses (6) |
| | Sagittal height/corneal topography | Visante, Spectralis and Pentacam | Study Visit Form for Scleral Lenses (6) |
| | Biomicroscopy | Slit-lamp with camera | Biomicroscopy Form (7) |
| | Auto-refraction | Auto-refractor | Study Visit Form for Scleral Lenses (6) |
| TRIAL LENS FITTING | | | |
| Lens fitting and examination | Slit lamp with camera | Study Visit Form for Scleral Lenses (6) | |

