| Vision assessment | LogMAR chart | Study Visit Form for Scleral Lenses (6) | |
| Lens fit evaluation (Clearance) | Visante and Spectralis | Study Visit Form for Scleral Lenses (6) | |
| Lens Delivery (Visits 1-1, 2-1) | Biomicroscopy/VA | Slit-lamp with camera/LogMAR | Biomicroscopy Form (7) and 6 |
| | LENS INSERTION, ASSESSMENT, DISPENSING AND QUESTIONNAIRE | | |
| | Lens examination | Slit lamp with camera | Study Visit Form for Scleral Lenses (6) |
| | Vision assessment | LogMAR chart | Study Visit Form for Scleral Lenses (6) |
| | Lens fit evaluation (clearance, etc) | Visante, Spectralis | Study Visit Form for Scleral Lenses (6) |
| | Tear Collection | Taken from Bowl of Scleral Lenses | Study Visit Form for Scleral Lenses (6) |

| | | | |
|--|---|-----------------------------------|---|
| | Ocular symptom questionnaire (2x) | Self-Administered Questionnaire | Ocular Symptom Questionnaire (8) |
| | Quality of life questionnaire (4x) | Self-Administered Questionnaire | CLIQ questionnaire (9) |
| | Subjective ratings | Analogue Scales | Wearing Habit Log Form (10) |
| Follow-up visit (Visits 1-2, 2-2) | Vision assessment | LogMAR chart | Study Visit Form for Scleral Lenses (6) |
| | Lens examination | Slit lamp with camera and K5M | Study Visit Form for Scleral Lenses (6) |
| | Lens Fit Evaluation (clearance) | Visante and Spectralis | Study Visit Form for Scleral Lenses (6) |
| | CONTACT LENS REMOVAL, ASSESSMENT, QUESTIONNAIRE REVIEW | | |
| | Tear Collection | Taken from Bowl of Scleral Lenses | Study Visit Form for Scleral Lenses (6) |
| | Biomicroscopy | Slit-lamp with Camera and K5M | Biomicroscopy Form (4) |
| | Sagittal height/topography | Pentacam and Spectralis OCT | Study Visit Form for Scleral Lenses (6) |
| | Osmolarity | Tearlab osmolarity system | Study Visit Form for Scleral Lenses (6) |
| | MMP-9 | InflammaDry | Study Visit Form for Scleral Lenses (6) |
| | Questionnaire Review | CLDEQ-8, CLIQ, Wearing log | Appendices 6,8 and 9 |
| | Participant exists study | - | Remuneration form |

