9 STATISTICAL ANALYSIS AND DATA MANAGEMENT

9.1 STATISTICAL ANALYSIS

All data described above will be analysed at the University of Waterloo from the eyes wearing the scleral lenses. Data analysis will be conducted using Statistica 13. Descriptive statistics will be used to analyse the baseline variables (age, gender, sagittal depth distribution, etc.). Table 3 lists the primary outcome variables and anticipated statistical procedures.

Table 3: Statistical procedures

| Variable | Analysis | Statistical test |
|---|---|------------------------------------|
| Parametric: tear clearance, corneal thickness, epithelial thickness, curvature, vision, osmolarity, comfort ratings | Comparison of lenses 1, 2 Comparison of epithelial and corneal thickness evaluation, osmolarity measurements | Paired t-test ANOVA RM-ANOVA |
| Nonparametric: OSDI, SPEED, CLDEQ-8, levels of protease | Comparison of ocular symptoms, quality of life, dryness, subjective assessment | T-test Mann-Whitney U test |

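### The in-clinic lens ratings at the two follow-up visits are set for the end of the visit, after the lens has been removed and the eye tested, while the follow-up procedures schedule no rating at all

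*Combined protocol and SAP*

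**What the plan says.** Section 4.3.11 defines the scales and their purpose: "Comfort, vision, dryness, burning and overall preference rating scales (0-100) will be used to assess the subjective responses for each of the contact lenses". It then sets the timing: "These subjective ratings will be done on a weekly basis (at home) and at the end of each study visit".

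Section 4.1.1 ties the follow-up visit to a stated amount of wear: "a single follow up visit after 8-10 hours of lens wear in a day, four weeks later (third visit". Section 4.4.2 applies the same 8-10 hours to both lens pairs, so it covers Visits 1-2 and 2-2. No such wear time is attached to the screening or delivery visits.

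Section 4.5.3 gives the order of the follow-up visit. After slit-lamp examination, visual acuity and OCT come removal and sampling: "The investigator will carefully remove the contact lens from the eye and immediately collect the tears from the lens bowl for tear analysis". Slit-lamp assessment of the cornea comes next, and then: "This will be followed by imaging with the Keratograph 5M (for staining) and Spectralis OCT for corneal thickness measurements". The questionnaires and grading scales come last, and they "will be collected and reviewed for completeness".

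Section 4.5.1 has the grading scales completed daily at home over four weeks of 8-10 hours' wear a day.

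Section 3 lists the subjective ratings under other variables of interest, outside the five primary outcomes. Its fourth objective is nevertheless the subjective rating of each lens pair. Table 3 in Section 9.1 includes comfort ratings among the parametric variables ("curvature, vision, osmolarity, comfort ratings").

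**The concern.** A rating meant to describe a lens is best made while the lens is on the eye and after a comparable period of wear. The follow-up visit offers that for both lenses: a clinic setting, a stated 8-10 hours of wear that day, and the same staff and sequence in each period. The timing rule in Section 4.3.11 moves the rating past that moment. By the end of the visit the lens is out, tears have been collected, and the eye has been examined and imaged. A vision rating that describes the present moment would then say nothing about the lens, and comfort, dryness and burning ratings could reflect the testing as well as the wear.

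The follow-up procedures add a second problem. They do not schedule the rating that Section 4.3.11 requires. Staff could follow either part of the protocol and believe themselves compliant, and the data would differ: a lens-out rating in one case, none in the other. At stake is the quality of the data for the fourth objective and for the planned comparison of comfort ratings between lenses.

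**Working it through.** No figure in the protocol bears on this point, so the check is to set the timing rules side by side.

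**1. Sequence at Visits 1-2 and 2-2**

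| Step | Section 4.5.3 | Table 2, follow-up block |
|---|---|---|
| Lens on | Slit lamp, visual acuity, Spectralis OCT | Visual acuity, lens examination, fit evaluation |
| Lens removed | Removal, then bowl tear collection at once | Block headed "CONTACT LENS REMOVAL, ASSESSMENT, QUESTIONNAIRE REVIEW", starting with tear collection |
| Lens off | Slit lamp, Keratograph, Spectralis OCT | Biomicroscopy, topography, osmolarity, MMP-9 |
| Last study item | Home forms collected and checked | Questionnaire review |

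Neither source describes putting the lens back in. A rating at the end of the visit therefore follows removal, sampling and testing. That the lens is out at that moment is an inference from this order; no sentence says so.

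**2. Is an in-clinic rating scheduled at follow-up?**

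Section 4.3.11 says yes. Section 4.5.3 and Table 2 list only the collection and review of forms already filled in. These do not agree.

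**3. Which other ratings fall within 8-10 hours of wear?**

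The home ratings do. Section 4.3.11 makes them weekly and Section 4.5.1 makes them daily, within a schedule of 8-10 hours' wear a day. No section gives the hour at which they are made, whether the lens is in, or whether the participant rates the moment or the day. The in-clinic follow-up rating is thus the only one at a visit tied to 8-10 hours of wear, but not the only one made during such a schedule.

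**4. What would reach the lens comparison?**

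Write A and B for the expected ratings under the two lenses, and c for a shift caused by testing that is the same after both. The within-participant difference is (A + c) − (B + c) = A − B, so a common shift cancels. What would not cancel is a loss of contrast because the lens is no longer felt or seen through, or added variability from the testing. The documents give no figure for either, and no effect size or standard deviation for the ratings.

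**5. Which rating is analysed?**

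Table 3 names comfort ratings and candidate tests, but not whether the analysed value is an in-clinic rating, a given week's home rating or a summary of several.

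**The case against.** The strongest reply is that the lens-out rating may never happen. Sections 4.5.2 and 4.5.3 and Table 2 treat the scales as take-home forms that are handed out, returned and checked. If practice follows those sections, the home ratings remain and nothing is rated with the lens out. The end-of-visit rating could also be retrospective: the scales concern responses to each lens, and overall preference can only be a judgement looking back. Appendix 10, which holds the log and scales, is not in the documents and may settle timing and wording. The ratings are also outside the primary list in Section 3.

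Much of this stands. It makes the harm uncertain and the priority moderate. It does not remove the written rule, which places the rating at a worse moment than the visit allows, or the conflict between that rule and the follow-up procedures. Nor do the home ratings settle the matter, since their frequency is contradictory and their hour and lens state are not given.

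A reader might infer several stronger things that the documents do not support:

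- **That the end-of-visit ratings are the only ones linked to 8-10 hours of wear.** Section 4.5.1 has the same scales completed at home during 8-10 hours' daily wear.
- **That the delivery visits have the same fault**, because tear collection precedes the ratings row in Table 2. That row cites the take-home wearing log and sits beside questionnaires marked 2x and 4x, which match biweekly and weekly completion over four weeks. It appears to be form dispensing.
- **That the screening visit yields a spoiled baseline rating.** Table 2 schedules no such rating there, and the coated-versus-uncoated comparison does not need one.
- **That a definite loss of power follows.** Any figure would rest on an invented fraction of the lens difference surviving removal, in a crossover where a shift common to both lenses cancels.
- **That a primary outcome is compromised.** The sentence introducing Table 3 calls its contents primary, but the table also holds variables, such as tear clearance and curvature, that Section 3 does not list as primary.

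**Conclusion.** The point holds in limited form. Followed literally, Section 4.3.11 has participants rate the lens at Visits 1-2 and 2-2 after it has been removed and the eye sampled and tested. Section 4.5.3 and Table 2 contain no such rating. The home ratings cover the wearing period, but their frequency is inconsistent and no hour of wear or lens state is given. The rating used for the lens comparison is not named.

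The size of any effect on the coated-versus-uncoated comparison is unknown. The conclusion rests on two assumptions: that the order of procedures in Section 4.5.3 and Table 2 is the order carried out, and that the lens is not reinserted before the end of the visit. It would weaken if the wearing log fixes the timing or asks explicitly about the wear just completed. Because the ratings serve a stated objective and a better moment is available at the same visit, the change is worth making. The ratings' place among the other variables of interest keeps it below the level of a threat to the trial's main outcomes.

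**What to change.** - **Section 4.3.11:** replace the end-of-visit rule for Visits 1-2 and 2-2 with a statement that the comfort, vision, dryness and burning ratings are made on arrival, with the study lens in place, before lens examination and removal.
- **Table 2:** add this rating as the first row of the follow-up block, and mirror it in Section 4.5.3, keeping it separate from the review of home forms.
- **Sections 4.3.11 and 4.5.1:** reconcile weekly with daily for the home ratings.
- **Section 9.1:** name the rating time point used for the coated-versus-uncoated comparison. If a home rating is chosen, give the hour of wear and the lens state at which it is made.

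The cost is a few sentences and one table row. The scales and visits stay the same, and a rating that Section 4.3.11 already requires moves to an earlier point in the visit.

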4.4 SCHEDULED AND UNSCHEDULED VISITS

This study has a total of 5 study visits, including the screening visit (see Table 1).

4.4.1 SCREENING AND TRIAL FITTING

The investigator will determine participant eligibility by reviewing the inclusion and exclusion criteria. The diagnosis of dry eyes will also be confirmed by OSDI and SPEED questionnaires (self-assessed at home and confirmed on first appointment), osmolarity and levels of protease (using inflammandry test kit) in the tear film. Ineligible participants will be advised that they do not meet the criteria for the study. If eligible, then the trial scleral and soft contact lens fittings will be performed following the manufacturer's recommended guidelines.

4.4.2 STUDY VISITS

This study will involve 5 visits over 5 study days in total. The total time commitment for all study visits is approximately 9 hours spread over a 3-month period (See Table 1). The total study visit time commitment may be different for each participant, as the needed visit time will depend on how easily the lenses can be fitted.

The first visit will involve screening and baseline measurements of the participants. The investigator will determine the eligibility of the participant using the inclusion/ exclusion criteria, questionnaires, and tear film analysis (osmolarity and protease levels). Ineligible participants will be discontinued from the study. Eligible participants will be trial fit with the most appropriate scleral lenses (Visit 0-0) as determined by the baseline measurements obtained at the screening visit/appointment. Tear collection from the ocular surface will also be performed as a baseline for comparison with collection from the scleral bowl in the dispensing and follow up visits with the scleral lenses. Participants will be instructed on insertion/application, removal, and proper handling and care of the lenses before dispensing the contact lenses (Visit 1-1, 2-1). Participants will be instructed on insertion, removal, and proper handling and care of the lenses before dispensing the contact lenses (Visit 1-1, 2-1). At each of the lens dispensing/delivery appointments, the researcher will dispense/deliver the study lenses and supplies (contact lens care system). Measurements including visual acuity, topographic corneal clearance, fluorescein assessment will be obtained while the participant is wearing the lenses. The tear collection (from the scleral lens bowl) will be collected immediately the lens is removed from the eye. Study questionnaires (CLDEQ-8, CLIQ and wearing habit/experience log along with the subjective grading scales) will also be handed out to the participants. These questionnaires will be filled each week and biweekly for each of the scleral lens pair for the four weeks wearing schedule.

After the participant has worn the lenses for 8 to10 hours during the day (2 pairs: uncoated scleral contact lens or Hydra-PEG coated scleral contact lens, randomly selected), the participant will return for a follow up visit four weeks later for each pair.

At each of the follow up appointments, evaluation of lens fit, measurements of corneal thickness and assessment of the cornea with slit-lamp biomicroscope will be repeated while the participant is wearing the lenses. Immediately after the scleral lens is removed, the tears will be collected from the bowl of the lens for analysis. Other primary outcome variables (e.g., other questionnaires) will also be collected and reviewed for completeness. (Visit 1-2, 2-2).

A wash-out period of minimum of 48 hours is required between the first lens, follow up visits and the second pair of lenses (scleral lenses). Table 1 Provides a summary of the study visits.

Table 1 Summary of the study visits.

| Visit code | Visits | Time |
|--|---|---------|
| 0-0 | Screening, baseline measurements and trial lens fitting | 2.5hrs |
| 1-1 | First lens delivery visit (scleral lenses with or without Hydra-PEG) - Lens 1 | 2.0hrs |
| 1-2 | Follow-up visit (scleral lenses with or without Hydra-PEG)- Lens 1 | 1.5 hrs |
| Wash-out Period (48hours minimum) | | |
| 2-1 | Second lens delivery visit (scleral lenses with or without Hydra-PEG)- Lens 2 | 1.5hrs |
| 2-2 | Follow-up visit (scleral lenses with or without Hydra-PEG)- Lens 2) | 1.5 hrs |

